## 1. SYNOPSIS

Trial Title	A Phase II Two-Arm Open-Label Study of Nivolumab plus Relatlimab or Ipilimumab in Metastatic Melanoma Stratified by MHC-II Expression.
Trial Sites	Vanderbilt University Medical Center and approximately 2 additional academic medical centers in the United States.
Overall Design	This is an open-label, non-randomized two arm Phase 2 study of intravenous nivolumab plus intravenous ipilimumab or intravenous relatlimab in patients with metastatic melanoma stratified by MHC-II expression.
Hypothesis	Patients with MHC-II expressing melanomas will have high rates of change in activated GZMB+ CD8+ T-cell density intratumorally with nivolumab and relatlimab therapy; MHC-II expression is an effective stratifying marker in melanoma that can be used in future studies to select optimal treatment.
Study Design	
Patients will be stratified into 2 arms: Arm A: MHC-II positive patients, and Arm B: MHC-II negative patients.
 
Arm A: Treatment will consist of cycles lasting 28 days (4 weeks) per cycle (nivolumab + relatlimab):
 
 
• On Day 1 of each 28-day cycle, all patients are scheduled to receive nivolumab and relatlimab intravenously.
 
 
Arm B: Treatment will consist of four initial cycles lasting 21 days (3 weeks) per cycle (nivolumab + ipilimumab); followed by cycles lasting 28 days (4 weeks) for nivolumab monotherapy:
 
 
• On Day 1 of cycles 1-4, all patients are scheduled to receive ipilimumab and nivolumab intravenously.
 
 
Starting with cycle 5, patients will receive nivolumab intravenously every 4 weeks.

Duration of Treatment	It is intended that patients will be treated until RECIST 1.1 confirmed disease progression, until intolerable toxicity, or up to a maximum of 2 years after initiation of study treatment.
Objectives and Efficacy Measures	
Primary Objective:
 
 
• To evaluate the efficacy, measured by change in activated GZMB+ CD8+ T-cell density intratumorally, of two immunotherapy regimens in patients with advanced melanoma: 
 
— nivolumab plus relatlimab in patients with MHC-II (+) melanoma, and
 
— nivolumab plus ipilimumab in patients with MHC-II (-) melanoma.
 
 
 
 
Secondary Objectives:
 
 
• To evaluate the response rate, median progression free survival, overall survival, and safety and tolerability of nivolumab plus relatlimab in patients with MHC-II (+) melanoma, and of nivolumab plus ipilimumab in patients with MHC-II (-) melanoma.
 

	
Exploratory Objectives:
 

• To explore potential associations of biomarkers with clinical efficacy and/or incidence of adverse events due to study drug by analyzing biomarker measures within the peripheral blood and tumor microenvironment.

 
Primary Efficacy Measure:
 

• Change in activated GZMB+ CD8+ T-cell density intratumorally.

 
Secondary Efficacy Measures:
 

• Response rate (RR)

• Median progression free survival (mPFS)

• Median overall survival (mOS)

• Adverse events.

Inclusion and Exclusion Criteria	See Section 5 .
Number of Patients and Study Duration	Approximately 36 evaluable patients accrued across 18 months (average accrual rate of 2 per month), with up to 2 years of survival follow-up. The total duration for study enrollment is estimated as 24 months.
Study Assessments	See the Schedule of Assessments in Section 7 .

## 2. SCHEMA

The study design schematic is presented in **Figure 1**:

Approximately 18 participants will be enrolled in each arm of the study. Accrual in a given arm will stop when 18 participants in the arm have enrolled. All participants may receive study treatment: until confirmed progression of disease, unacceptable toxicity, participant withdrawal of consent, or study closure.

The study will consist of three phases: screening, treatment, and follow-up as detailed below.

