### **5.4. Number of Patients and Replacement of Patients Who Discontinue Early**

Approximately 36 evaluable patients with advanced melanoma are anticipated to enroll in this study at Vanderbilt University Medical Center and approximately two additional academic medical centers in the U.S.

In general, it intended that patients will be treated until confirmed disease progression or intolerable toxicity. The criteria for patient discontinuation are listed in [Section 9.9](#).

If a patient discontinues protocol treatment in the first cycle for reasons clearly not related to protocol treatment after completing fewer than 1 planned cycle of study therapy, then that patient will be considered not evaluable for toxicity and will be replaced with a new patient.

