### **18.2. Sample Size and Power**

The primary endpoint for this study is change in GZMB+ CD8+ T cell infiltration. A total sample size of 36 with 18 in each arm will provide 83% power to detect a difference in mean activated CD8+ T cell density change of one standard deviations (e.g., 1 SD=1000 counts/mm^2 is roughly the effect size for doubling T cell count), with a two-sided significance level of 0.05. Assuming a 10% dropout rate, a total number of 40 patients is planned for enrollment in the study to ensure the study has adequate statistical power for the primary analysis.

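### Section 2 closes each arm at 18 enrolled, but Section 18.2 plans 40 enrolled so that 18 per arm remain after 10% dropout

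*Combined protocol and SAP*

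**What the plan says.** Four places in the combined protocol and SAP give patient numbers.

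- **Section 2 (Schema):** "Accrual in a given arm will stop when 18 participants in the arm have enrolled". The sentence before it says approximately 18 per arm, but the stop itself carries no such qualifier and counts enrolled patients, not evaluable ones.
- **Section 18.2 (Sample Size and Power):** "A total sample size of 36 with 18 in each arm will provide 83% power" for a between-arm difference of one standard deviation at a two-sided 0.05 level. It goes on: "Assuming a 10% dropout rate, a total number of 40 patients is planned for enrollment in the study".
- **Section 1 (Synopsis):** about 36 evaluable patients over 18 months at 2 per month. It then adds: "The total duration for study enrollment is estimated as 24 months".
- **Section 5.4:** "Approximately 36 evaluable patients with advanced melanoma are anticipated to enroll in this study". It replaces a patient only for discontinuation in the first cycle that is clearly unrelated to treatment, and it ties this to evaluability for toxicity.

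Arms are not assigned by randomisation. The synopsis states: "Patients will be stratified into 2 arms: Arm A: MHC-II positive patients, and Arm B: MHC-II negative patients".

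**The concern.** Sections 2 and 18.2 both count enrolled patients, and they give 36 and 40. Section 2 is the only explicit accrual stop in the documents, and Section 6 has sites verify slot availability with the Coordinating Center before enrolment. It is therefore the rule that would be applied in practice. Applying it discards the margin that Section 18.2 adds to protect power for the primary analysis.

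The replacement rule in Section 5.4 does not restore that margin. The primary endpoint needs an on-treatment biopsy at about week 6 (Section 8.13: Cycle 2 Day 15 in Arm A, Cycle 3 Day 1 in Arm B). A patient who stops for toxicity, leaves after the first cycle, or has no usable biopsy is lost to that endpoint without being replaced. The documents also do not say whether a replacement may exceed the cap of 18.

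**Working it through.** **Inputs.** From Section 18.2: standardised difference d = 1 (1 SD, given as 1000 counts/mm²), two-sided alpha 0.05, 18 per arm, 10% dropout, 40 enrolled. From Section 18.4: a two-sample t-test. From Section 2: a stop at 18 enrolled per arm.

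**Formula.** For n₁ and n₂ analysed patients, df = n₁ + n₂ − 2, noncentrality δ = d / √(1/n₁ + 1/n₂), and c is the 0.975 quantile of t with df degrees of freedom. Power = 1 − F(c; df, δ) + F(−c; df, δ), where F is the noncentral t distribution function.

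**Step 1: reproduce the plan's figures.**
- 18 vs 18: δ = 1/√(2/18) = 3.00, df = 34, c = 2.032, power 83.0%. This matches the stated 83%.
- Enrolment: 36/0.9 = 40, or 18/0.9 = 20 per arm. This matches the stated 40.

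**Step 2: apply the Section 2 stop at 10% loss.** Expected evaluable per arm is 18 × 0.9 = 16.2.
- 17 vs 17: 80.7%.
- 16 vs 16: δ = 1/√(2/16) = 2.83, df = 30, c = 2.042, power 78.1%.
- Averaged over independent binomial loss in each arm, no replacement: 78.4%.
- Half the dropouts replaced (net loss 5%): 80.8%.
- All dropouts replaced: 83.0%.

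The documents do not give the share that would be replaced, so the last three figures form a range, not an estimate. With no replacement, an arm capped at 18 keeps all 18 with probability 0.9¹⁸ = 15%, and both arms do so with probability 0.9³⁶, about 2%.

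**Step 3: compare like for like** (10% loss, averaged, no replacement, all evaluable patients analysed).
- 20 enrolled per arm: 82.8%.
- 18 enrolled per arm: 78.4%.
- Gap: 4.4 points. It is 4.1 points at 5% loss and 4.7 at 20%.

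For scale, a true effect of 0.95 SD instead of 1 SD (an assumption) would cost about as much: 79.1% at 18 vs 18.

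**Step 4: should the 40 be a total or a per-arm stop?** Arms follow MHC-II status, so a bare total of 40 could fill unevenly. At 10% loss, averaged, power is 81.2% at 24/16 enrolled and 75.9% at 28/12.

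**Step 5: accrual time.** The synopsis rate gives 18 × 2 = 36 patients. No MHC-II prevalence is stated, so take as assumptions 2 enrollable patients per month overall and a share p for the smaller group. Months to fill the slower arm = n/(2p).

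| p | 18 per arm | 20 per arm |
|---|---|---|
| 50% | 18.0 | 20.0 |
| 40% | 22.5 | 25.0 |
| 30% | 30.0 | 33.3 |

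The synopsis's 24 months suffices for 20 per arm only if p is at least 20/48 = 41.7%, and for 18 per arm only if p is at least 18/48 = 37.5%.

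**The case against.** The strongest reply is that one sentence in Section 2 is out of line and the rest of the plan is coherent. About 36 evaluable is what 40 enrolled yields at 10% dropout, and 24 months at 2 per month would allow 48 patients. This stands: the synopsis and Section 5.4 are silent on the 40 and do not form a second contradiction. They also do not resolve the first one.

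The power range can be challenged at both ends. The 83% end needs every dropout replaced, which Section 5.4 does not provide, so it is only a bound. At the lower end, Section 6 cancels the registration of a patient who does not start treatment within the allowed 7 days, and that may free a slot. Some of the 10% might then not use up the 18. The documents do not say how much, so this could soften the 78% but does not remove the conflict.

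A stop at 20 enrolled also does not guarantee 18 evaluable in each arm. At independent 10% loss one arm reaches 18 with probability 0.677, and both with 0.677² = 46%. That is correct, but average power is still 82.8%, because some arms finish with 19 or 20. A stop at 18 evaluable per arm would secure the number itself, at the price of an open enrolment total.

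Finally, Section 3.7 says that the arms are evaluated in parallel and not compared, which limits the weight of a few points of between-arm power. Yet Section 18.2 sizes the study on a between-arm difference, Section 18.4 provides for testing between-group differences, and fewer biopsy pairs reduce precision within each arm as well.

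**Conclusion.** The concern holds. A stop at 18 enrolled per arm and a plan to enrol 40 cannot both be followed, and no other provision reconciles them. Under the Section 2 stop, between-arm power is about 78% with no replacement and at most 83% with full replacement, a loss of 0 to about 5 points against the stated figure. This rests on the plan's own inputs (1 SD difference, two-sided 0.05, 10% dropout), on losses that are independent between patients, and on all evaluable patients being analysed. The size is modest, but the rule that decides when enrolment closes should not be ambiguous. It should be fixed.

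**What to change.** **Preferred.** Change the Section 2 stop to 20 enrolled per arm, the even split of the 40 in Section 18.2, and analyse every patient with evaluable baseline and week-6 density. In the synopsis and Section 5.4, state about 40 enrolled to obtain about 36 evaluable. Keep the stop per arm and not as a total of 40. State also whether patients replaced under Section 5.4 count within the 20; the cost below assumes that they do.

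**Alternative.** Keep the stop at 18 enrolled, delete the 40 from Section 18.2, and restate the power as about 78%, up to 83% depending on replacement.

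**Cost.** Either route needs a written amendment approved by the sponsor-investigator and each site's IRB (Section 16.1). The preferred route uses no patients beyond the 40 already planned. It adds about 2 months of accrual if the arms fill equally, or 2.5 to 3.3 months if the smaller group's share is 40% to 30% (assumed). The alternative adds no accrual time and costs only a less favourable stated power.

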### 2.1. Screening Phase

- Begins by signing of the informed consent form (ICF) and establishing the participant's eligibility.
- Participant is assessed for complete study eligibility as described in [Section 5](#).
- A pregnancy test for WOCBP documented within 72 hours prior to the start of the first dose of study medication.
- Tumor tissue must be received at Vanderbilt University Medical Center (VUMC) for MHC-II testing in order for the participant to be enrolled in the correct arm of the study. MHC-II positivity is defined as  $\geq 5\%$  of tumor cells expressing MHC-II.

### 2.2. Treatment Phase

- Begins upon subject's initiation of protocol-indicated treatment.
- Arm A: Nivolumab 480 mg IV and Relatlimab 160mg IV are administered on day 1 of every 4 week cycle until disease progression, discontinuation due to unacceptable toxicity, withdrawal of consent or study closure, or 104 weeks of treatment.
- Arm B: Nivolumab 1mg/kg IV and Ipilimumab 3mg/kg IV are administered on day 1 of every 3 week cycle for 4 doses. Then, nivolumab 480mg IV is administered on day 1 of every 4 week

---

cycle until disease progression, discontinuation due to unacceptable toxicity, withdrawal of consent or study closure, or 104 weeks of treatment.

- Treatment beyond initial investigator-assessed RECIST 1.1-defined progression is permitted if the subject has investigator-assessed clinical benefit and is tolerating treatment.
- Study assessments are to be collected as outlined in [Section 7](#).
- This phase ends when the participant is discontinued from study therapy or at a maximum of 2 years of treatment.

### **2.3. Post-treatment Follow-up Phase**

- Begins after 2 years of treatment or when the decision is made to discontinue a participant from study therapy.
- Subjects who discontinue treatment for reasons other than disease progression will continue to have tumor assessments (if clinically feasible) according to the schedule in [Section 7](#) until progression or the start of any subsequent therapy, whichever occurs first.
- Subjects will be followed for drug-related toxicities until these toxicities resolve, return to baseline or are deemed irreversible. All treatment-related serious adverse events will be documented for a minimum of 100 days after the last dose of study.
- After completion of the follow-up visit, subjects will be followed every 3 months ( $\pm$  14 days) after patient's last dose of study treatment – until death, end of the study, until lost to follow-up or patient withdraws consent, or for a maximum of 2 years after a patient's final study treatment—whichever comes first. Survival contact can be made via clinic visit, chart review, obituary or similar observation (e.g. Social Security death index), or by telephone. The sponsor-investigator and/or BMS may request that survival data be collected on all treated subjects outside of the protocol defined window. At that time of this request, each subject will be contacted to determine their survival status unless the subject had withdrawn consent for all contact.
- Study assessments are to be collected as outlined in [Section 7](#).

## **3. BACKGROUND AND RATIONALE**

### **3.1. Introduction**

Advanced melanoma is historically associated with a dismal prognosis and limited therapeutic options. Recently, advances in targeted and immune therapies have resulted in durable responses for nearly half of treated patients. In particular, immune checkpoint inhibitors have driven long-term responses for a substantial fraction of treated patients. Despite this, both intrinsic and acquired resistance remains a major limitation and at least half of patients still die of metastatic disease.

Immune checkpoint inhibitors are agents that remove negative regulators of T cell responses. Immune checkpoints are terms for molecules such as programmed death-1 (PD-1), programmed death-ligands 1 (PD-L1) and 2 (PD-L2) that downregulate the host anti-tumor immune response, and are expressed in many cancer types. Thus, these molecules play a key role in evading anti-tumor immunity.

Nivolumab (also referred to as BMS-936558 or MDX1106) is a human monoclonal antibody (HuMAb; immunoglobulin G4 [IgG4]-S228P) that targets the PD-1 cluster of differentiation 279 (CD279) cell surface membrane receptor. PD-1 is a negative regulatory molecule expressed by

activated T and B lymphocytes. Binding of PD-1 to its ligands, PD-L1 and PD-L2, results in the down-regulation of lymphocyte activation. Inhibition of the interaction between PD-1 and its ligands promotes immune responses and antigen-specific T-cell responses to both foreign antigens as well as self-antigens. Nivolumab has recently shown clinical efficacy in numerous cancers, including melanoma, renal cell carcinoma, NSCLC, Hodgkin lymphoma, and others.

Recent studies have also conclusively demonstrated that combining ipilimumab, an inhibitor of cytotoxic T lymphocyte antigen-4, increases the response rate and progression free survival in patients with metastatic melanoma. The response rate was 58% vs. 43% vs. 19% for the combination, nivolumab, and ipilimumab respectively ( $p<0.001$ ), while median PFS was similarly improved (median 11.5 vs. 6.9 vs. 2.9 months,  $p<0.001$ ). Overall survival was also increased numerically (58% vs. 52% at 3 years), although this was not statistically significant. Still, the same limitations of intrinsic and acquired resistance still occur, limiting the effectiveness of therapy in many patients.

Despite the activity of nivolumab and ipilimumab + nivolumab in these studies, markers to prospectively identify patients most likely to respond are needed. Early studies suggested that expression of PD-L1 was required for response to nivolumab, however subsequent studies have not confirmed this. Importantly, when PD-L1 was examined in patients treated with nivolumab or ipilimumab+ nivolumab, no difference in PFS was observed. This contrasted with patients with low PD-L1 expression, which correlated with improved PFS in the combination. However, overall survival was not statistically different in either group, and response rate was superior for the combination in both groups. Overall, PD-L1 positivity correlates with response to therapy, but does not allow accurate response prediction. Thus, better predictive biomarkers are needed to stratify patients to immunotherapy treatment, particularly in the first-line setting.

Nivolumab and relatlimab has also demonstrated efficacy in patients with advanced melanoma. Among heavily pre-treated patients, all of which had previously failed single-agent anti-PD-1 therapy, a response rate of 11.5% was observed (7 of 61), with a disease control rate of 49%. Biomarker analyses suggested that subjects whose TIL expressed more LAG-3 had a higher response rate, with a greater than 3-fold increase in ORR observed in subjects with evidence of LAG-3 expression in at least 1% of nucleated cells within the tumor margin, compared to less than 1% LAG-3 expression (18.2% [6/33] and 5.0% [1/20], respectively). PD-L1 expression did not appear to enrich for response.

### **3.3. Rationale for Nivolumab and Relatlimab in Melanoma**

Relatlimab (also referred to as BMS-986016, BMS-986016-01, and anti-lymphocyte activation gene 3 [LAG-3]) is a fully human LAG-3-specific IgG4 antibody. Relatlimab binds to the LAG-3 receptor with high affinity, and thus blocks LAG-3 interactions with its known ligand, major histocompatibility complex (MHC) Class II, which is the peptide antigen presentation molecule recognized by CD4+ T cells. Relatlimab binding inhibits the negative regulatory function of LAG-3 in vitro. By blocking the downregulatory pathway, relatlimab enhances the anti-tumor immune response and, thus, has the potential to inhibit the growth of multiple malignancies when administered as a single agent or in combination with other therapeutic immuno-oncology (IO) monoclonal antibodies (mAbs). Using surrogate antibodies recognizing mouse LAG-3 (C9B7W and 19C7), anti-tumor activity mediated by LAG-3 blockade has been demonstrated in 3 murine syngeneic in vivo tumor models (Sa1N fibrosarcoma, MC38 colon adenocarcinoma, and A20 B-cell lymphoma). Both tumor inhibition and the number of tumor-free mice were increased by anti-LAG-3 monotherapy, while the combination of anti-LAG-3 with a blocking anti-programmed cell death protein 1 (PD-1) antibody provided enhanced anti-tumor activity higher than the activity of either agent alone and higher than the activity of anti-cytotoxic T-lymphocyte-associated protein 4 (CTLA-4) antibody in some mice. Several other studies have clearly demonstrated the role of LAG-3, and the additive effects of PD-1 and LAG-3 blockade both in pre-clinical models of cancer and chronic infection.

Single agent studies using relatlimab (CA224020 and CA224022) demonstrated partial responses in non-small cell lung cancer and marginal zone lymphoma, with numerous other patients showing stable disease. Relatlimab in combination with nivolumab has shown the capacity to induce responses in previously heavily treated advanced solid tumors, with the added ability to trigger responses in tumors that have demonstrated resistance to nivolumab therapy. As of the cutoff date of 15-Jun-2017 for Part B of Study CA224020, in subjects treated with relatlimab and nivolumab combination therapy, partial responses were seen in subjects with melanoma, cervical cancer, NSCLC, and squamous cell carcinoma of the head and neck (SCCHN). As of the cutoff date of 07-Apr-2017 for Study CA224022 in subjects treated with relatlimab and nivolumab combination therapy, partial responses have been seen in subjects with relapsed/refractory Hodgkin lymphoma, with stable disease observed in 1 subject for 6 months (and treatment was continuing). In subjects with melanoma treated with relatlimab and nivolumab combination therapy in Part C of Study CA224020, the overall objective response rate (ORR) was 11.5% (7/61, response evaluable) with a disease control rate of 49%. Biomarker analyses suggested that

subjects whose TIL expressed more LAG-3 had a higher response rate, with a greater than 3-fold increase in ORR observed in subjects with evidence of LAG-3 expression in at least 1% of nucleated cells within the tumor margin, compared to less than 1% LAG-3 expression (18.2% [6/33] and 5.0% [1/20], respectively). PD-L1 expression did not appear to enrich for response.

The safety profile of nivolumab + relatlimab has been largely similar to nivolumab monotherapy. LAG-3 knockout in mice has minimal effects, but combination PD-1 and LAG-3 knockout leads to multiorgan autoimmunity. This result has not been recapitulated in humans. Overall, among 304 patients treated with this combination, 157 (51.6%) had at least one treatment related event, most commonly fatigue (12.2%), diarrhea (6.6%; grade 3 in 1%), pruritus (6.9%), and infusion reaction (5.9%). One patient had a grade 5 event (myocarditis); 10.2% had grade 3-4 toxicities.

**TABLE 2: Summary of Adverse Events Reported in At Least 5% of Subjects During Combination Therapy in Study CA224020, Parts B and C (N = 304)**

Preferred Term	All AEs (Regardless of Causality)			Drug-related AEs		
	Any Grade AEs n (%)	Grade 3 - 4 AEs n (%)	Grade 5 AEs n (%)	Any Grade AEs n (%)	Grade 3 - 4 AEs n (%)	Grade 5 AEs n (%)
Total Subjects with an Event	256 (84.2)	76 (25.0)	48 (15.8)	157 (51.6)	31 (10.2)	1 (0.3)
Fatigue	69 (22.7)	4 (1.3)	0	37 (12.2)	0	0
Malignant Neoplasm Progression	47 (15.5)	3 (1.0)	42 (13.8)	0	0	0
Diarrhoea	41 (13.5)	3 (1.0)	0	20 (6.6)	3 (1.0)	0
Nausea	40 (13.2)	0	0	12 (3.9)	0	0
Asthenia	39 (12.8)	1 (0.3)	0	7 (2.3)	0	0
Pyrexia	38 (12.5)	1 (0.3)	0	13 (4.3)	1 (0.3)	0
Decreased Appetite	34 (11.2)	1 (0.3)	0	6 (2.0)	0	0
Dyspnoea	33 (10.9)	4 (1.3)	0	10 (3.3)	2 (0.7)	0
Arthralgia	32 (10.5)	0	0	17 (5.6)	0	0
Cough	31 (10.2)	0	0	4 (1.3)	0	0
Constipation	30 (9.9)	0	0	1 (0.3)	0	0
Anaemia	28 (9.2)	9 (3.0)	0	1 (0.3)	0	0
Abdominal Pain	25 (8.2)	6 (2.0)	0	5 (1.6)	0	0
Vomiting	24 (7.9)	1 (0.3)	0	2 (0.7)	0	0
Headache	23 (7.6)	0	0	5 (1.6)	0	0
Pruritus	23 (7.6)	0	0	21 (6.9)	0	0
AST Increased	21 (6.9)	5 (1.6)	0	12 (3.9)	4 (1.3)	0
Back Pain	20 (6.6)	1 (0.3)	0	4 (1.3)	0	0
ALT Increased	18 (5.9)	4 (1.3)	0	11 (3.6)	2 (0.7)	0
Infusion Related Reaction	18 (5.9)	0	0	18 (5.9)	0	0
Myalgia	16 (5.3)	0	0	6 (2.0)	0	0
Rash	16 (5.3)	0	0	11 (3.6)	0	0

Notes: MedDRA Version 20.0, CTC Version 4.0; includes events reported between the first dose and 135 days after the last dose of study treatment. All reported AEs were as of the database lock on 15-Jun-2017.

CTC = Common Toxicity Criteria; MedDRA = Medical Dictionary for Regulatory Activities.

Source: Study CA224020, BMS\_GBS\CA224\BYA62589\Biostatistics\Production\Tables\rt-ae-all.sas Run Date: 07JUL2017:12:08, BMS\_GBS\CA224\BYA62589\Biostatistics\Production\Tables\rt-ae-allrel.sas Run Date: 07JUL2017:12:09

